Study design: This is a pilot feasibility 2x2 factorial design randomized clinical trial at the University of Michigan. The study duration will be three years.

Study population and participants: Registrants of the T1D Exchange, a national T1D patient registry, will be approached for recruitment. Adults with T1D, using continuous glucose monitor (CGM) ≥ 1 year and continue to experience ≥ 1 severe hypoglycemic episode (SHE) OR spending $\geq 1\%$ of time in level 2 hypoglycemia will be recruited.

Intervention: All eligible participants will undergo a 2-week basic hypoglycemia education. Four possible experimental conditions (10 weeks) will be randomly assigned to participants in 1:1:1:1 ratio: (1) Hypoglycemia symptom detection training+psychoeducation; (2) hypoglycemia symptom detection training only; (3) psychoeducation only; (4) usual care. The entire intervention phase will last 12 weeks.

Endpoints: Outcomes of mHealth technology integrity (e.g., connectivity to CGM data, message delivery), intervention fidelity and acceptability (message reading and acceptability) and trial conduct (e.g., recruitment, retention, outcome assessment) will be collected. The primary outcome is the number of people to recruit to reach to n=20 completing the intervention.

Scheduled activities:

	Pre-screening (Pre-consent)	Recruitment	Week 0 (baseline)	Week 2	Week 6	Week 12	Week 26	Week 52
Demographics	X							
Clinical and diabetes history	X							
Severe hypoglycemia history	X		X			X	X	X
CGM data collection	X		X			X	X	X
Eligibility criteria confirmation		X						
Informed consent		X						
Hypoglycemia symptom detection; confirmation; beliefs; management intention setting; decision and action to manage hypoglycemia			X			X	X	X
Interceptive awareness			X					
Advanced diabetes technology changes			X	X	X	X	X	X
Randomization/Intervention initiation			X					
Feasibility Outcome Evaluation								
mHealth technology integrity outcomes			X	X	X	X		
Intervention fidelity and acceptability outcomes								
Intervention fidelity			X	X	X	X	X	X
Intervention acceptability						X		
Trial conduct outcomes								
Feasibility of protocol and recruitment conduct	X	X	X	X	X	X	X	X
Feasibility of outcome measurements			X			X		
Participation compensation feedback						X		
Safety Evaluation								
Pregnancy Reporting			X	X	X	X	X	X
Adverse events reporting			X	X	X	X	X	X
Diabetic ketoacidosis reporting and CGM hyperglycemia assessment			X	X	X	X	X	X

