- **Potential risks:** The most likely risk to participants is the time burden associated with participation in the study. We do not expect study-related text messages and collections of patient demographics, CGM data and patient reported outcomes through self-reporting instruments to significantly increase participants' health risks to higher than they would otherwise experience in their ordinary daily life. Other potential risks include the breach of confidentiality or data security ("rare"). Some participants may experience distress from the content of text messages about hypoglycemia. Patients will be informed that they can stop from participating in the trial if they do not want to continue with the study.
- **Potential benefits:** An impactful and widely accessible hypoglycemia behavioral intervention program can improve hypoglycemia self-management and reduce hypoglycemia and related complications and burdens. If this mHealth program is effective, participants may also experience reduction in hypoglycemia.
- **Assessment:** Participants will be exposed to no more than minimal risk while the information gained could help develop an impactful program to reduce life-threatening hypoglycemic events.

2. Study design

Trial design overview, setting, and schema

This is a pilot 2x2 factorial design randomized clinical trial at the University of Michigan. All candidates will undergo pre-screening and consent procedures prior to recruitment. After recruitment and baseline assessment, all participants will undergo randomization and a 2-week basic hypoglycemia education. Subsequently, based on randomization results, four possible experimental conditions will be implemented in participants in 1:1:1:1 ratio: (1) Hypoglycemia symptom detection training+psychoeducation; (2) hypoglycemia symptom detection training only; (3) psychoeducation only; (4) usual care. Each experimental condition will last 10 weeks. After the end of the intervention, all participants will undergo the 40-week follow-up phase with conduct at 26th week and 52nd week to complete the 52-week study.

Randomization, allocation, and blinding

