Adaptive randomization with minimization method will be conducted to ensure equal number of participants (n=10) will be randomized into the same number of the 4 experimental conditions (i.e., in 1:1:1:1 ratio). The randomization will be stratified based on whether the participant have severe hypoglycemia within the year OR spending ≥1% of time in level 2 hypoglycemia on CGM, and the status of closed-loop pump use. The procedure of randomization will be determined by the study statistician.

The experimental condition allocation mechanism will be generated by the study statistician and held by the PI. When a participant is recruited, the study coordinator will collect the allocation information from the PI and assign the allocation to the participant.

Even randomization errors are not expected, when they occur, we will apply the intention-to-treat principle and include the affected participant into the analysis. When needed, we may also work with the Data and Safety monitor, who will provide independent, objective assessment, and under the previously published guidance,⁷ and consider removing affected participants.

This study will not use blinding given complete blinding participants and study investigators from the intervention (i.e., education content) participants receives will not be possible.

End-of-study definition

The end of the study is defined as completion of the 52-week follow-up assessment.

3. Study population

Eligibility criteria

- Inclusion criteria:
 1. Provision of signed and dated informed consent form
 2. Age 18-70
 3. Self-reported diagnosis of type 1 diabetes for at least 5 years
 4. Previous attendance of structured diabetes education program
 5. Using CGM ≥1 year
 6. Ongoing Dexcom CGM use time ≥70% based on CGM report at screening
 7. Have had experienced ≥1 episode of SH in the past year while using CGMs OR spending ≥1% of time in level 2 hypoglycemia at the time of pre-screening
 8. Using cellphone with functionality for sharing real-time data to Dexcom Clarity and receiving text messages
 9. Be able to communicate in English (spoken and written)
 10. Willing to comply with all study procedures including sharing CGM glucose information, receiving and reading intervention text messages, and completing study questionnaires
- Exclusion criteria:

1. Active participation in clinical trials on diabetes/hypoglycemia interventions
2. Pregnancy or planning for pregnancy within a year

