 - Reasons eligible participant for not consenting
 - Average time delay from prescreening to enrollment
 - Average time delay from enrollment to intervention initiation
 - Retention:
 - Rate of participant retention (at 12 weeks) (a secondary outcome)
 - Rate of participant retention (at 26 weeks) (a secondary outcome)
 - Rate of participant retention (at 52 weeks) (a secondary outcome)

- Percentage of participants discontinuing study intervention
- Reasons for participants to be discontinuing study intervention
- Percentage of participants discontinued from the study (including the loss of follow-up)
- Reasons for participants to be discontinued from the study (intervention duration, assessment burdensome, treatment condition, etc)
- Compensation fairness
 - Percentage of participants found the compensation fair
- Feasibility of outcome measurements:
 - Percentage of participant changing advanced diabetes technologies during the study
 - Percentage of participants with CGM data collected (at 12 weeks) (a secondary outcome)
 - Percentage of participants with CGM data collected (at 26 weeks) (a secondary outcome)
 - Percentage of participants with CGM data collected (at 52 weeks) (a secondary outcome)
 - Percentage of participants with questionnaires completed at 12 weeks
 - Percentage of participants with questionnaires completed at 26 weeks
 - Percentage of participants with questionnaires completed at 52 weeks
 - Percentage of people finding self-reported instrument having too many questions to answer
 - Percentage of people finding self-reported instrument taking too much time
 - Percentage of people finding self-reported instrument too tiring to complete
 - Other feedback from study coordinators including training protocol

Safety and adverse events

- This protocol uses the definition of adverse event and classification of adverse event, the relationship between the adverse events with the study procedures, and the expectedness of the adverse event from 21 CFR 312.32 (a), which could be found on website:
<https://www.accessdata.fda.gov/scripts/cdrh/cfdocs/cfcfr/cfrsearch.cfm?fr=312.32>

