- The occurrence of an adverse event (AE) or serious adverse event (SAE) may come to the attention of study personnel during scheduled study contacts with participants or upon review by a study monitor. All AEs, not otherwise precluded per the protocol, will be captured on the appropriate case report form (CRF). Information to be collected includes event description, time of onset, clinician's assessment of severity, relationship to study procedures (assessed only by those with the training and authority to make a diagnosis), and time of resolution/stabilization of the event. All AEs occurring while on study will be documented appropriately regardless of relationship. All AEs will be followed to adequate resolution.
- Any medical or psychiatric condition that is present at the time that the participant is screened will be considered as baseline and not reported as an AE. However, if the study participant's condition deteriorates at any time during the study, it will be recorded as an AE.
- Changes in the severity of an AE will be documented to allow an assessment of the duration of the event at each level of severity to be performed. Documentation of onset and duration of each episode will be maintained for AEs characterized as intermittent.
- Diabetes-related complications including diabetic ketoacidosis are unexpected adverse events that may not be related to the study intervention. These adverse events will be monitored but will not be reported. If the rate of these adverse events appears to be higher than expected, the study team will discuss with study monitor about whether to put the study on hold to decide the next steps.
- Study coordinators will record events with start dates occurring any time after informed consent is obtained until 7 (for non-serious AEs) or 30 days (for SAEs) after the last day of study participation. At each study visit, the investigator will inquire about the occurrence of AE/SAEs since the last visit. Events will be followed for outcome information until resolution or stabilization.

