The study team will meet weekly to review study issues. We will maintain a record of protocol deviation and review it every 3 months for any unusual patterns. An official review of study data, protocol adherence, and safety, including severe adverse events, will be conducted by the PI, the study coordinator and the Data and Safety Monitor(s) after every 5 participants have completed the study. If the Data and Safety Monitor(s) have serious concerns with participant data or safety integrity, study activities will be halted and plans for addressing these issues will be developed to continue the study, or the decision to terminate the study will be made in consultation with the IRB. Additional meetings/conferences with the study team/mentors will be made as needed to discuss problems and make recommendations as an ongoing process throughout the study. No interim analysis will be conducted for this pilot/feasibility study.

Stop rule: The study will be terminated if the risk-to-benefit ratio is higher than expected.

Data Integrity: Data integrity of the study will be monitored through an electronic data system (REDCap). This electronic data system will prompt data entry or show visual signals if there are data missing and to be filled. Additional measures (e.g., number range or selection box) will be implemented to minimize data entry errors. The database will be tested before its actual use in research. Documentation integrity will also be reviewed after every 5 participants have completed the study procedure as discussed above.

Privacy and Confidentiality: Procedures to protect privacy and confidentiality, such as using unique numeric identifiers for subject identification, collecting information limited to the amount necessary for the study, and storing data in a HIPPA-compliant database (REDCap), will be implemented. The electronic data will be accessible only to investigators and study team members. The data will be available for review by the FDA or any other authorized governmental agencies.

Safety Monitoring: The occurrence of adverse events (AEs) will be sought by non-directive questioning of the patients at recruitment and study end. At the time of enrollment, participants will be provided contact information for questions or AE reporting. A review of AEs or severe adverse events (SAEs) will take place after every 5 participants have completed the study.

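### Distress from message content is a named risk, but no outcome or scheduled safety item asks about it, and the sections on when adverse events are asked about disagree

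*Combined protocol and SAP*

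**What the plan says.** Section 1 (Risk/benefits assessment) lists time burden, loss of confidentiality, and one risk that comes from the content of the intervention: "Some participants may experience distress from the content of text messages about hypoglycemia". The stated response is that participants may leave the trial.

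On eliciting adverse events, the plan speaks in three places:

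- Section 6, Data and Safety Monitoring Plan (Safety Monitoring): "The occurrence of adverse events (AEs) will be sought by non-directive questioning of the patients at recruitment and study end". Participants also receive contact details for reporting events.
- Section 6, Safety and adverse events: "At each study visit, the investigator will inquire about the occurrence of AE/SAEs since the last visit". The form of the question is not stated.
- Protocol Summary, Scheduled activities: the row "Adverse events reporting" is marked at weeks 0, 2, 6, 12, 26 and 52.

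Section 2 fixes study end: "The end of the study is defined as completion of the 52-week follow-up assessment".

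The other safety rows of the schedule are pregnancy and "Diabetic ketoacidosis reporting and CGM hyperglycemia assessment". The acceptability outcomes in Section 6 are whether content was found helpful and how many messages arrived per day. Reasons for leaving are collected: "Reasons for participants to be discontinued from the study (intervention duration, assessment burdensome, treatment condition, etc".

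**The concern.** The plan attributes one content-related harm to its own messages and then provides no item that asks about it. Ketoacidosis and hyperglycemia, by contrast, have their own scheduled row, although Section 6 says ketoacidosis may be unrelated to the intervention.

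The risk is plausible from the plan's own description. The detection messages follow each sensor-detected episode and invite the participant to recall it. The psychoeducation works on risk perception and draws on belief challenging and exposure techniques (Section 4). Someone mildly upset by a text may not think of it as an adverse event and may not mention it when asked a general question.

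The pilot is meant to inform acceptability and the later effectiveness trial. If distress is not asked about, a low count will be hard to interpret, and the pilot will have little to say about a possible explanation for non-reading or dropout, both of which it does measure.

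**Working it through.** **1. Where distress could be recorded.**

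| Route | Where | Does it ask about distress? |
|---|---|---|
| Adverse-event inquiry at visits | Section 6, Safety; schedule | No, general inquiry |
| Non-directive questioning | Section 6, Safety Monitoring | No, by its nature |
| Spontaneous report | Section 6, Safety Monitoring | No, participant must volunteer it |
| Alert when a participant texts a stop reply | Section 6, technology outcomes | No, and only those who opt out |
| Reasons for discontinuing | Section 6, Retention | Not listed, though the list is open; only those who stop |
| Acceptability | Section 6 | No: helpfulness and message count |
| Scheduled self-report constructs | Schedule | None named as distress, anxiety or fear |

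The questionnaires are not itemised, so absence is judged on the text available.

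**2. Timing.** The intervention ends at week 12 (2 weeks of basic education plus 10 weeks). Study end is week 52. If the Safety Monitoring paragraph governed, the first adverse-event question after messaging began would come 52 − 12 = 40 weeks after the intervention ended. Under the schedule and the Safety section there are contacts at weeks 2, 6 and 12, during or at the end of messaging. Both cannot describe the same procedure.

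**3. Number exposed.** Section 7 plans up to 40: 4 conditions × 10 = 40, which reproduces. Recruitment may stop once 20 have completed. Section 4 sends the basic hypoglycemia messages to every participant, usual care included, so the exposed group is up to 40, not just the 3 × 10 = 30 in the three component conditions.

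**4. Illustration of under-recording (assumed inputs).** The documents give no distress rate *p* and no capture proportion *s*. Treating participants as independent, the chance of recording no case among *n* is (1 − *p·s*)^*n*. For example, with *p* = 10%, *s* = 50%, *n* = 20: (1 − 0.05)^20 = 35.8%.

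| Assumed *p* | *n* | *s* = 25% | *s* = 50% | *s* = 100% |
|---|---|---|---|---|
| 5% | 20 | 77.8% | 60.3% | 35.8% |
| 10% | 20 | 60.3% | 35.8% | 12.2% |
| 20% | 20 | 35.8% | 12.2% | 1.2% |
| 5% | 40 | 60.5% | 36.3% | 12.9% |
| 10% | 40 | 36.3% | 12.9% | 1.5% |
| 20% | 40 | 12.9% | 1.5% | <0.1% |

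The range is too wide to support any single figure. It shows only that a count of zero could arise in several quite different ways.

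**5. What a direct item would allow.** If it captured every case and none were reported, the one-sided 95% upper bound is 1 − 0.05^(1/*n*):

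- *n* = 20: 1 − 0.05^(1/20) = 13.9%
- *n* = 40: 1 − 0.05^(1/40) = 7.2%

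The two-sided exact 95% interval uses 0.025 in place of 0.05 and has upper limits of 16.8% and 8.8%. For one condition with 0 of 10, the upper limit is 1 − 0.025^(1/10), about 31%.

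**The case against.** A reader might infer that adverse events are sought only by non-directive questions. The documents do not support that. Section 6 has the investigator ask at each visit without calling that inquiry non-directive, the schedule marks six time points, and all events are to be documented whatever their relationship to the study. Pregnancy and ketoacidosis are targeted. Participants can report on their own initiative, a stop reply alerts the team, and the list of discontinuation reasons is open-ended and so already admits distress.

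A reader might also infer that distress is likely to be missed, or that the pilot will report none. That too goes beyond the text. That general questions miss mild emotional reactions is a reasonable expectation, but the documents do not state it, and several assumed combinations above make at least one recorded case the more probable result. Nor is the minimal-risk statement shown to be wrong: it denies a *significant* increase in risk, which mild distress would not contradict, and the risk itself is disclosed.

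There are mitigations as well. People with uncontrolled mental disorder are excluded, and the messages are described as positively framed and respectful of autonomy.

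All of this stands, and it limits the point to a possibility of under-recording. It does not remove the gap, because none of these routes prompts for distress, and the only questioning style the plan specifies is one that "will be sought by non-directive questioning of the patients". The conflict over timing is untouched by these arguments.

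**Conclusion.** The point holds in a limited form. Distress is a named risk of the messages, no outcome or scheduled item asks about it, and it may therefore be under-recorded. By how much cannot be derived from the documents; across assumed rates of 5% to 20% and capture of 25% to 100%, the chance of recording no case runs from under 0.1% to 77.8%, depending on numbers enrolled. The contradiction between the Safety Monitoring paragraph and the schedule and Safety section is plain on the page and needs no assumption.

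This is a worthwhile, low-cost improvement to a descriptive pilot. It does not affect the primary outcome or the sample size.

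**What to change.** 1. **Add one direct item** to the week 2, 6 and 12 contacts, which already ask about message reception and reading (Section 4, Fidelity measures). It should ask whether any messages upset or worried the participant, with graded answers from not at all to a lot. Ask all participants, usual care included. Week 2 falls at about the end of the common basic education, and weeks 6 and 12 cover the assigned condition.
2. **Report** the overall percentage with an exact 95% interval, stating how many answered and which answers count as positive. Give counts by condition descriptively only, because 10 per condition is too few for useful intervals.
3. **Assess positive answers** under the existing adverse-event definitions, rather than recording each one automatically as an adverse event.
4. **Reconcile** the timing of adverse-event questions in Section 6 (Safety Monitoring) with Section 6 (Safety and adverse events) and the Scheduled activities table.
5. **Optional:** name distress among the discontinuation reasons. The list is already open-ended, so this only helps consistent coding.

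The cost is one question in contacts that already take place, one table row and an edit to one paragraph. The downside is that more mild events will be recorded and will need assessment.

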Fidelity measures: **Text message delivery, reception and reading** will be checked for fidelity. For text message **delivery**, a log of the text messages (with content and time stamps) delivered to each participant will be available on the HypoPals mHealth program website and will be monitored weekly to ensure correctness of the content and time delivered during the intervention period. We will contact participants at, 2, 6 and 12 weeks, either through telephone calls or text messages, to confirm timely **reception** of these text messages. When contacting participants, we will also evaluate self-reported text message **reading** based on regularity (e.g., from right away to ignoring it completely) and completeness (from the whole message to not at all), with an adapted mSustain survey.¹⁶ A log of participants' responses to the two-way interactive text messages will also be available on the mHealth program website and the rate of responding will also be used for fidelity assessment. During the telephone visits at weeks 0, 2, 6, 12, 26 and 52, we will also verbally assess whether the participant has changes in diabetes care including receiving additional diabetes and hypoglycemia-related interventions.

Rescue therapy

Rescue therapy will not be applied to this study as there currently exists no widely available program for reducing hypoglycemia. All study subjects will continue receiving their current care from their diabetes healthcare providers for hypoglycemia management.

5. Intervention and participant discontinuation

Discontinuation of study intervention

The study intervention will be discontinued if:

- The researcher believes that it is not in the participant's best interest to stay in the study.
- Participant becomes ineligible to participate.
- Participant's condition changes and needs treatment that is not allowed while taking part in the study.
- Participant deviates from or do not follow instructions from the researchers.
- The study is suspended or canceled.

The reason(s) for discontinuing the participant from the intervention will be documented.

When a participant discontinues from study intervention but not from the study, remaining study procedures will be completed as indicated by the study protocol.

Discontinuation from the study

An investigator may discontinue a participant from the study for the following reasons:

- Significant study intervention non-compliance, unless varying compliance is an aspect of the study objectives

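### One stopping bullet makes ending the intervention mandatory for not following instructions, without the threshold and exemption in the next list, although the pilot measures poor reading as fidelity

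*Combined protocol and SAP*

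**What the plan says.** Section 5 has two adjacent lists.

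- *Discontinuation of study intervention* opens with "The study intervention will be discontinued if". One of its five conditions is "Participant deviates from or do not follow instructions from the researchers".
- *Discontinuation from the study* opens with "An investigator may discontinue a participant from the study for the following reasons". Its matching item is "Significant study intervention non-compliance, unless varying compliance is an aspect of the study objectives".

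After a stop, "The reason(s) for discontinuing the participant from the intervention will be documented", and "When a participant discontinues from study intervention but not from the study, remaining study procedures will be completed as indicated by the study protocol". Section 5 also says that people who leave before the intervention phase ends are replaced.

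Section 4 (Fidelity measures) says "We will contact participants at, 2, 6 and 12 weeks" and grades self-reported reading "based on regularity (e.g., from right away to ignoring it completely". Replies to two-way messages are logged. Section 6 makes reading at the end of the intervention a secondary outcome and the two-way response percentage a fidelity outcome. It also reports how many participants stop the intervention and why. The primary outcome is how many people must be recruited for 20 to complete the intervention. Inclusion criterion 10 (section 3) asks for willingness to follow the study procedures, and reading the messages is one of those it names. Section 7 allows up to 40 enrolled, 10 per condition.

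**The concern.** The protocol recognises, in the study list, that compliance may be something a trial is there to observe. That recognition is missing from the list that switches the messages off, and that list is the mandatory one. Fidelity is part of this pilot's stated objective, so variation in reading and responding is a result to be reported.

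Staff who apply the bullet literally could learn of poor reading at week 2 or week 6, before the week-12 assessment, and conclude that they must stop the messages. Two results would be exposed. The person no longer completes the intervention, so one more recruit is needed and a protocol rule appears as poor feasibility. Also, section 6 does not say how people stopped early enter the end-of-intervention reading percentage.

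**Working it through.** **1. The two lists compared**

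| | Stopping the intervention | Leaving the study |
|---|---|---|
| Force | mandatory | discretionary |
| Degree of non-compliance | none stated | significant |
| Exemption where compliance is under study | none | yes |

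No other part of the document limits the intervention bullet.

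**2. Does the bullet reach poor readers?** The chain has three links.

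- Reading is a named study procedure (criterion 10).
- Poor reading can be seen at weeks 2 and 6, and non-response in the log (section 4).
- Not reading counts as not following the researchers' instructions. No text says this; it is inferred from criterion 10, which tests willingness at entry.

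The conclusion is therefore conditional: a literal application *could* remove poor readers.

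**3. Primary count**

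- The plan's own figure reproduces: 4 conditions × 10 = 40. Reaching 20 completers from 40 needs 20/40 = 50% completion.
- I take it that a person stopped by staff has not completed the intervention. With *s* stops of people who would otherwise have completed, the count is 20 + *s*. One stop gives 21, and 21/20 = 1.05.
- The replacement sentence stands under leaving the study, so it may not cover someone who stops only the intervention. The count rises either way, because it is defined by completing the intervention.
- Illustration with assumed rates: let *c* be the completion rate otherwise and *q* the share of would-be completers stopped under the bullet. Then *p* = *c*(1 − *q*), the average number of recruits needed is 20/*p*, and the chance of at least 20 completers among 40 is a binomial tail.

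| *c* | *q* | *p* | 20/*p* | P(at least 20 of 40) |
|---|---|---|---|---|
| 80% | 0 | 0.80 | 25.0 | about 1.00 |
| 80% | 10% | 0.72 | 27.8 | 0.999 |
| 80% | 20% | 0.64 | 31.25 | 0.976 |
| 80% | 30% | 0.56 | 35.7 | 0.822 |

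Over *c* from 70% to 90% and *q* from 0 to 30%, 20/*p* runs from 22.2 to 40.8. The documents give neither rate. Poor readers who would have dropped out anyway do not count towards *q*.

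**4. Reading percentage**

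Three of the four conditions send messages after week 2. With 20 to 40 enrolled and an even split, that is 15 to 30 people. Assume 80% read: 12/15 or 24/30.

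| Handling of stopped non-readers | 15 people | 30 people |
|---|---|---|
| Kept in the denominator | 12/15 = 80% | 24/30 = 80% |
| One left out | 12/14 = 85.7% | 24/29 = 82.8% |
| Two left out | 12/13 = 92.3% | 24/28 = 85.7% |

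The shift appears only if stopped people are left out. The 15-person column is approximate: with 20 completers and one stop, at least 21 would have been enrolled.

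**The case against.** The strongest reply is that the protocol, read as a whole, treats poor reading as data. The reading scale runs down to ignoring messages completely, it is used at three time points, and response rates are named as a fidelity measure. Instructions from the researchers could just as well mean sharing CGM data or completing questionnaires. This largely stands. It makes removal of poor readers less likely, but the mandatory bullet still does not say that they stay.

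A reader might go further and infer that the protocol orders poor readers off the messages. The documents do not support that, because no text defines reading or answering a message as an instruction.

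A reader might also infer that the reading percentage will be overstated. That needs staff to stop the person before week 12 and analysts then to drop that person. Section 6 speaks of participants and does not restrict the measure to completers. Study procedures continue after a stop, so the week-12 contact should still take place, and stops and their reasons are reported. What remains is an unstated denominator; a bias is not shown.

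Finally, keeping someone who ignores every message counts that person as a completer and makes recruitment look easier. Which count better informs the next trial is a judgement. The protocol should make that choice openly, and a loosely worded stopping bullet does not.

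**Conclusion.** The inconsistency between the two lists is plain in the text. Its consequence is conditional on staff reading the bullet literally and treating non-reading as a failure to follow instructions. If they do, each stop of a would-be completer adds one to the primary count, or 5% on a base of 20. In most of the assumed scenarios the limit of 40 leaves room for this. At the extreme (70% completion, 30% stopped) the average need is 40.8 and the chance of 20 completers is about 0.51. Any effect on the reading percentage depends on dropping stopped people, which the plan does not say it will do.

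The true size is unknown, because every completion, reading and stopping rate used here is assumed. The study is descriptive and tests no hypothesis, and no safety issue arises. The severity is minor, but the wording is worth correcting before the pilot runs.

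**What to change.** Reword the intervention bullet so that it requires significant non-compliance with study instructions and carries the same exemption as the study list. Add that not reading or not answering messages is recorded as fidelity data and is not by itself a reason to stop.

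In section 6, state that anyone whose intervention is stopped stays in the denominator of the end-of-intervention reading percentage. Show missing week-12 values as a separate category and do not impute them. Scoring stopped people as non-readers would be wrong, since someone can read without replying or be stopped for another reason. Carrying a week-2 value forward would also mislead, because all messages up to then are basic education.

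The cost is the wording of one bullet and one stated denominator. Reading, response logs and reasons for stopping are already collected. The downside is that reported fidelity may be lower and completers will include some people who read little.
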